### 1.3. Schema

Figure 1: Trial Diagram

See Section 5.5.3 for dose and escalation scheme CCI

b The Safety Follow-up Visit (SFV) is only required for patients who prematurely discontinue treatment or for patients who complete the trial and do not enroll in the Long-Term Extension (LTE) or Bridging Visits.

c Patients who complete the trial and trial assessments may be eligible to participate in the LTE (or receive open-label setmelanotide and attend Bridging Visits if the LTE is not yet available).

CCI

## 2. INTRODUCTION

### 2.1. Background

Hypothalamic obesity (HO) is a severe, devastating disease of obesity that may be either acquired due to injury to the hypothalamus or be part congenital disorder (including early developmental disease) that involves the hypothalamus. Acquired HO affects approximately 5,000 to 10,000 patients in the United States (US) and is believed to have similar incidence and prevalence in the European Union and rest of world (EU; [Teng 2021](#); [Roth 2015](#)).

Acquired HO develops after injury to the hypothalamus, most often as a result of a tumor (eg, craniopharyngiomas, gliomas, pituitary adenomas, hamartomas), and/or the surgery or radiation therapy used to treat the tumor ([Hochberg 2010](#)). Other much rarer causes of injury include inflammatory conditions involving the hypothalamus such as sarcoidosis or trauma.

Craniopharyngiomas represent the most common tumor associated with the development of HO and account for 5% to 15% of pediatric intracranial tumors, and occur with 2 peaks of incidence, one during childhood (10 to 19 years of age [29%]) and the second in adulthood (30 to 49 years of age [25%]) ([Muller 2022](#)).

Patients with acquired HO develop an aggressive form of obesity characterized by a high degree of sudden, severe, and sustained weight gain that is generally unresponsive to lifestyle or medical intervention. The weight gain is most dramatic in the first 6-12 months after injury and then continues for the next 8 to 12 years before plateauing ([Sterkenburg 2015](#)). Hyperphagia may occur in approximately 50% of patients along with lethargy due to decreased energy expenditure, and psychosocial disorders spanning from depression to aggressive behavior ([Muller 2011](#)).

CCI

CCI

Central melanocortin signaling has been extensively discussed as the primary element of energy homeostasis (Holland 2019). In patients with hypothalamic lesions or deficiencies, leptin signaling is often disturbed and results in reduced melanocortin signaling. This has been associated with hyperphagia and excessive weight gain. (Enriori 2016; Roth 2010; Roth 1998; Patel 2002; Shaikh 2008). In patients with craniopharyngioma or post-surgical treatment for it, for example, levels of alpha-melanocortin-stimulating hormone ( $\alpha$ -MSH) were found to be significantly reduced (Roth 2010; Roth 2011). Reduced serum  $\alpha$ -MSH levels suggest melanocortin pathway deficiency, which might explain lower energy expenditure in peripheral tissues due to reduced fat and muscle fatty acid oxidation (Roth 2010; Roth 2011; An 2007).

Setmelanotide, a potent melanocortin 4 receptor (MC4R) agonist, is a synthetic 8 amino acid, cyclic peptide that binds with high affinity to the human MC4R and is efficient in activating MC4R. While not an analog, it retains the specificity and functionality of the naturally occurring pro-opiomelanocortin (POMC)-derived neuropeptide,  $\alpha$ MSH, which is the endogenous ligand for the MC4R.

Setmelanotide is authorized for marketing in several regions including the US, UK, Israel, the EU, and Canada. Additional information is available in the current Investigator's Brochure (IB).

Setmelanotide is under continued clinical investigation globally for the treatment of various rare diseases of obesity as well as acquired diseases resulting in obesity such as HO that are demonstrated or hypothesized to impact signaling in the hypothalamic MC4R pathway. There is currently no effective treatment for HO.

## **2.2. Trial Rationale**

Data obtained to date in the setmelanotide clinical program demonstrate robust weight reduction and hunger suppression efficacy in obesity disorders that impact signaling in the leptin-melanocortin pathway, such as POMC deficiency, LEPR deficiency, and BBS, as well as obesity disorders caused by hypothalamic injury such as HO (Phase 2 Trial RM-493-030).

By restoring impaired signaling in this pathway, setmelanotide can serve as an indirect form of replacement therapy for patients with hypothalamic deficiencies (both acquired and congenital) that lead to extreme obesity, with the potential for improvements in body weight and appetite control.

## **2.3. Benefit/Risk Assessment**

Data generated in the Phase 2 proof of concept trial RM-493-030 have indicated a favorable efficacy response profile, specifically in HO patients treated with setmelanotide. Given the observed clinical benefit of setmelanotide in adults and children with HO and a consistent well-understood adverse event (AE) profile, it is considered that setmelanotide will have a positive benefit-risk profile in patients with HO who currently have no other long-term successful therapeutic options. In patients with rare genetic forms of obesity, setmelanotide has been associated with clinically meaningful reductions in weight, improvement in hunger, as well as improvements in quality of life.

Setmelanotide has been well tolerated by patients in clinical studies. The AEs associated with setmelanotide are predictable, well understood, and do not present significant safety concerns. Safety data obtained to date show that AEs commonly associated with setmelanotide include injection site reactions, skin hyperpigmentation, nausea and headaches. Less commonly, vomiting was reported and, rarely, sexual events have been observed (this study will collect information on these known events related to the study drug in detailed case report forms to obtain as much information as possible in the HO population). Potential mechanistic-based events such as hypertension have not been observed throughout the setmelanotide clinical development program. Events associated with severe obesity such as depression and suicidal ideation occurred infrequently and were assessed as not related to setmelanotide.

More detailed information about the known and expected benefits and risks and reasonably expected AEs of setmelanotide may be found in the IB.

### 3. OBJECTIVES AND ENDPOINTS

The objectives and endpoints are summarized in Table 3.

CCI

**Table 3: Objectives and Endpoints**

Objective	Endpoint
Primary	
To evaluate the efficacy of setmelanotide on change in body mass index (BMI)	– Mean % change in BMI from Baseline after approximately 52 weeks on a therapeutic regimen of setmelanotide compared to placebo
Key Secondary	
To evaluate the efficacy of setmelanotide on proportion of patients with $\geq 5\%$ reduction in BMI or $\geq 0.2$ -point reduction in BMI Z-score	
 
– The proportion of patients with <math>\geq 5\%</math> reduction in BMI in adult patients (<math>\geq 18</math> years of age), or BMI Z-score reduction of <math>\geq 0.2</math> points in pediatric patients (<math>< 18</math> years of age) from Baseline after approximately 52 weeks on a therapeutic regimen of setmelanotide compared to placebo
 
– The proportion of all patients with <math>\geq 5\%</math> reduction in BMI from baseline after approximately 52 weeks on a therapeutic regimen of setmelanotide compared to placebo
 

To evaluate changes in hunger in response to setmelanotide	– Mean change in the weekly average of the daily most hunger score in patients $\geq 12$ years old from Baseline after approximately 52 weeks on a therapeutic regimen of setmelanotide compared to placebo
Secondary	
To evaluate changes in hunger and in symptoms of hyperphagia in response to setmelanotide	
 
– The proportion of patients with a <math>\geq 2</math>-point reduction in the weekly average of the daily most hunger score from Baseline after approximately 52 weeks on a therapeutic regimen of setmelanotide compared to placebo
 
– Mean change in the weekly average of the Symptoms of Hyperphagia composite score from Baseline after approximately 52 weeks on a therapeutic regimen of setmelanotide compared to placebo
 

To evaluate changes in additional parameters of body weight	
 
– The proportion of patients with a <math>\geq 10\%</math> reduction in BMI from Baseline after approximately 52 weeks on a therapeutic regimen of setmelanotide compared to placebo
 
– The proportion of patients with a <math>\geq 10\%</math> reduction in weight from Baseline after approximately 52 weeks
 

**Table 3: Objectives and Endpoints**

Objective	Endpoint
	
on a therapeutic regimen of setmelanotide compared to placebo
 
 
– Mean percent change in weight in patients <math>\geq 18</math> years from Baseline after approximately 52 weeks on a therapeutic regimen of setmelanotide compared to placebo
 
– Mean BMI Z-score and BMI percentile reduction in patients <math>< 18</math> years of age from Baseline after approximately 52 weeks on a therapeutic regimen of setmelanotide compared to placebo
 
– The proportion of patients aged <math>\geq 4</math> to <math>< 18</math> years with <math>\geq 0.2</math>-point reduction of BMI Z-score from Baseline after approximately 52 weeks on a therapeutic regimen of setmelanotide compared to placebo
 
– The proportion of patients with BMI <math>< 30</math> kg/m^2 (patients aged <math>\geq 18</math> years) or <math>< 95^{\text{th}}</math> percentile (patients aged <math>< 18</math> years) from Baseline after approximately 52 weeks on a therapeutic regimen of setmelanotide compared to placebo
 

To evaluate changes in quality of life in response to setmelanotide treatment	
 
– Mean change in physical functioning score and total score for the Impact of Weight on Quality of Life-Lite (IWQOL) (IWQOL-Lite-CT in patients <math>\geq 18</math> years and IWQOL-Kids in patients 11 to <math>< 18</math> years), from Baseline after approximately 52 weeks on a therapeutic regimen of setmelanotide compared to placebo
 

To evaluate changes in waist circumference following treatment with setmelanotide compared to placebo	
 
– Change in waist circumference from Baseline after approximately 52 weeks on a therapeutic regimen of setmelanotide compared to placebo
 

To evaluate changes in cardiometabolic parameters following treatment with setmelanotide compared to placebo	
 
– The difference in change in cardiometabolic parameters including BP, CCI [REDACTED], liver function and CCI [REDACTED] from Baseline after approximately 52 weeks on a therapeutic regimen of setmelanotide compared to placebo
 

**Table 3: Objectives and Endpoints**

Objective	Endpoint
Safety	
To evaluate the safety and tolerability of setmelanotide compared to placebo	– Safety and tolerability assessed by the frequency and severity of adverse events (AEs), AEs of special interest (AESIs), vital signs, and laboratory evaluations from Baseline after approximately 52 weeks on a therapeutic regimen of setmelanotide compared to placebo
To evaluate the effect of setmelanotide on blood pressure (BP)	– Change in ambulatory BP and heart rate (HR) from Baseline after approximately 52 weeks on a therapeutic regimen of setmelanotide compared to placebo (in patients $\geq 12$ years)

CCI

CCI

CCI

CCI

## 4. SELECTION AND WITHDRAWAL OF PATIENTS

Prospective approval of protocol deviations to recruitment and enrollment criteria (ie, protocol waivers or exemptions) is not permitted.

### 4.1. Inclusion Criteria

Inclusion criteria are detailed below. CCI

Patients must meet all of the following criteria to be eligible for trial participation:

1. Patient has documented evidence of acquired HO defined as:
  - CCI
2. Aged 4 years and older at time of enrollment
3. Documented weight gain associated with the hypothalamic injury either before therapy or following therapy (surgery and/or following chemotherapy or radiotherapy), and a body mass index (BMI) of  $\geq 30$  kg/m^2 for patients  $\geq 18$  years of age, or BMI  $\geq 95^{\text{th}}$  percentile for age and sex for patients 4 to  $<18$  years of age based on the US Centers for Disease Control and Prevention criteria.
4. Patients must meet the contraception requirements outlined in Section 6.8.9 unless otherwise indicated.
5. Ability to communicate well with the Investigator, understand and comply with the requirements of the trial, and understand and sign the written informed consent and/or assent for patients aged  $<18$  years, a parent/legal guardian that can sign.
6. If receiving hormone replacement therapy (ie, thyroid hormones, glucocorticoids, growth hormone or other medications known to affect metabolism or weight/body composition), the dose of such therapy has remained stable for at least 2 months prior to Screening.  
Note:
  - Changes in dose of  $\leq 25\%$  may be permissible, with the Sponsor's approval. If results of free thyroxine (FT4) warrant changes in therapy  $>50\%$  or the addition of new medication the patient is screen failed and can be reassessed after 2 months.
  - This does not apply to patients experiencing adrenal crisis.

CCI

## 4.2. Exclusion Criteria

Patients meeting any of the following criteria are not eligible for trial participation:

1. Diagnosis of Prader-Willi syndrome (PWS) or Rapid-onset obesity with hypoventilation, hypothalamic, autonomic dysregulation, neuroendocrine tumor syndrome (ROHHADNET).
2. Weight loss >2% in the previous 3 months for patients aged  $\geq 18$  years or >2% reduction in BMI for patients aged 4 to <18 years.

NOTE: Dietary and/or exercise regimens, with or without the use of medications, supplements or herbal treatments associated with weight loss (eg, orlistat, lorcaserin, phentermine, topiramate, naltrexone, bupropion, glucagon-like peptide-1 [GLP-1] receptor agonists, etc) are allowed if:

- the regimen and/or dose has been stable for at least 3 months prior to randomization
- the patient has not experienced weight loss >2% (for patients  $\geq 18$  years) or >2% BMI (for patients aged 4 to <18 years) during the previous 3 months, and

- the patient intends to keep the regimen and/or dose stable throughout the course of the trial.

***Note: This exclusion criterion applies only to initial study screening and is not applicable at the time of the inclusion/exclusion review for the LTE (or Bridging).***

3. Bariatric surgery or procedure (eg, gastric bypass/band/sleeve, duodenal switch, gastric balloon, intestinal barrier, etc) within the last 2 years. All patients with a history of bariatric surgery or procedures must be discussed with and receive approval from the Sponsor prior to enrollment.
4. Diagnosis of severe psychiatric disorders (eg, schizophrenia, bipolar disorder, personality disorder), or Major Depressive Disorder (MDD) within the previous 2 years, or Screening Patient Health Questionnaire (PHQ)-9/PHQ-A score  $\geq 15$ , or any suicidal ideation of type 4 or 5 on the Columbia-Suicide Severity Rating Scale (C-SSRS), or a Children's Depression Inventory-2 (CDI-2) T-score  $\geq 70$  during Screening, or lifetime history of suicide attempts, or any suicidal behavior in the last month.
5. Glycated hemoglobin (HbA1c)  $> 11.0\%$  at Screening.
6. Current, clinically significant pulmonary, cardiac, metabolic, or oncologic disease considered severe enough to interfere with the trial and/or confound the results. Any patient with a potentially clinically significant disease should be reviewed with the Sponsor or contract research organization (CRO) monitor to determine eligibility.
7. End stage renal disease (GFR  $< 15$  mL/min/1.73 m^2) in any age or glomerular filtration rate (GFR)  $< 30$  mL/min/1.73 m^2 during Screening in patients  $< 12$  years of age (GFR calculated using the Bedside Schwartz Formula for patients  $< 18$  years of age).
8. Significant dermatologic findings relating to melanoma or pre-melanoma skin lesions (excluding non-invasive basal or squamous cell lesion), determined as part of a comprehensive skin evaluation performed by the Investigator during Screening. Any concerning lesions identified during Screening will be biopsied and results known to be benign prior to enrollment. If the pre-treatment biopsy results are of significant concern, the patient is not eligible for trial participation.
9. History or close family history (parents or siblings) of skin cancer or melanoma (not including noninvasive, infiltrative basal or squamous cell lesion), or patient history of ocular-cutaneous albinism.
10. Participation in any clinical trial with an investigational drug/device within 3 months or 5 half-lives, whichever is longer, prior to the first trial dose.
11. Previously enrolled in a clinical trial involving setmelanotide or any previous exposure to setmelanotide.
12. Inability to comply with once daily (QD) injection regimen.
13. Pregnant and/or breastfeeding or desiring to become pregnant during this trial.
14. Patients with obesity attributable to other genetic or syndromic conditions (eg, PPL [POMC, PCSK1, LEPR, collectively], BBS) prior to the hypothalamic injury.

15. Cognitive impairment that, in the Investigator's opinion, precludes participation in the trial and completion of trial procedures or questionnaires.
16. Patient is, in the Investigator's opinion, otherwise not suitable to participate in the trial.
17. Legally protected persons per local regulations (eg, those that fall under the L1121-6 article of the Public Health Code in France).
18. The patient or a relative of the patient is the Investigator or a sub-investigator, research assistant, pharmacist, study coordinator, or other staff directly involved with the conduct of the trial.
19. Hypersensitivity to setmelanotide and/or any excipients contained in the investigational drug.

CCI

**CCI**  

#### **4.3. Treatment Discontinuation and Withdrawal from Trial**

Given this rare patient population, every effort should be made to encourage and keep patients enrolled in the trial until completion, unless there are any safety concerns necessitating withdrawal of the trial treatment or the patient from the trial. If patients must discontinue

treatment, they should be encouraged to continue to participate in all regular trial visits and assessments (other than dosing and pharmacokinetic [PK] assessments), if possible, as a Retained Dropout.

The Sponsor will provide assistance for patient and caregiver travel and will provide other necessary logistical support to ease the burden on the patient in order to facilitate compliance and completion of trial participation.

Discontinuation of trial treatment or skipped visits/doses may be allowed without withdrawal from the trial upon consultation with the Sponsor and CRO Medical Monitor.

Patients who either discontinue treatment or withdraw from the trial before completing the trial are to attend an Early Termination of Treatment (ETT) Visit as soon as possible after the last dose of trial treatment. Patients who prematurely discontinue treatment may also be required to complete the Safety Follow-up Visit (SFV), if applicable (Section 5.1.4).

If the ETT Visit occurs 4 weeks or later following the last dose of trial treatment, then the ETT Visit will replace the SFV if no ongoing AEs are being monitored. Patients who prematurely discontinue study drug treatment will continue to complete all scheduled study visits for assessments following completion of the ETT.

Patients who complete the trial will have the opportunity to participate in the LTE with open-label setmelanotide (or Bridging visits if the LTE is not yet available). Patients must meet the LTE eligibility criteria and should discuss eligibility with the Investigator.

Patients who discontinue trial treatment but remain in the trial should be encouraged to attend all planned visits until the final Visit. See Section 5.1.3. Patients who discontinue treatment will be counted as non-responders, irrespective of treatment assignment. Patients who discontinue treatment prematurely are not eligible to enroll in the optional LTE. Exceptions may be made in consultation with the Sponsor.

Patients who withdraw from the trial will attend an ETT visit only.

If the patient withdraws consent for disclosure of future information, the Sponsor may retain and continue to use any data collected before such a withdrawal of consent.

If a patient withdraws from the trial, he/she may request destruction of any samples taken and not tested, and the Investigator must document this in the site trial records and inform the Sponsor.

Patients will be informed that they have the right to withdraw from the trial at any time for any reason, without prejudice to their medical care. The Investigator also has the right to withdraw patients from the trial for reasons such as:

- AEs, which in the opinion of the Investigator justifies treatment or trial withdrawal. For specific predefined events, additional monitoring and guidance for the Investigator is provided in [Appendix 5](#).
- Non-adherence to trial medication regimen or protocol requirements.
- Non-compliance with instructions or failure to return for follow-up.

All patients who withdraw prior to completing the treatment period should be strongly encouraged to complete the ETT visit as outlined in the SoAs (Table 1, CCI ), even if they are no longer receiving trial medication.

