#### 5.1.3. End of Treatment

The End of Treatment (EOT) visit will occur as an in-person clinic visit after 52 weeks on a therapeutic regimen, which is the final planned week of dosing with trial treatment. At the EOT, patients who complete 52 weeks on a therapeutic regimen and complete assessments through the EOT visit may be eligible to enter an open-label LTE trial or attend Bridging visits with open-label setmelanotide if the LTE is not yet available. Patients must meet the LTE eligibility criteria and should discuss eligibility with the Investigator.

CCI

All patients who discontinue treatment prematurely should attend an ETT Visit as soon as possible after the last dose of trial treatment. Patients who discontinue treatment but remain enrolled in the trial should continue to complete assessments (as Retained Dropouts). These patients will be required to complete the SFV as applicable following the ETT (Section 5.1.4). Patients who discontinue treatment prematurely are not eligible to enroll in the optional LTE trial. Exceptions may be made in consultation with the Sponsor.

Patients who discontinue prematurely and withdraw from the trial will not be required to complete the SFV following the ETT.

If the ETT Visit occurs 4 weeks or later following the last dose of trial treatment, then the ETT Visit will replace the SFV if no AEs are being monitored.

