hypothesis requires the rejection of the null hypothesis at the 2-sided 0.05 significance level. The statistical criterion corresponds to the 2-sided 95% CI for the mean difference (setmelanotide – placebo) excluding 0 (ie, upper bound of the CI <0).

The primary analysis will be conducted based on the mITT population and sensitivity analysis based on the PP may be conducted as appropriate. Multiple Imputation approach assuming missing not at random (MNAR) will be used as the primary approach for missing values and will model the missing measurements based on known measurements from retrieved dropouts in the same treatment group. Should there be insufficient retrieved dropouts to provide a reliable multiple imputation model, then the wash-out imputation method will be used where missing values for subjects on active drug will be imputed with observed baseline and data from the placebo group. No intermediate values from the active treatment group will be used in the imputation.

The primary efficacy analysis will be based on the treatment policy estimand approach, in which all patients, regardless of intercurrent events, continue to be measured at each prespecified clinical visit unless consent to collect such data is explicitly withdrawn, and in which all such measurements are included in the statistical analyses.

To assess the sensitivity of results to the primary missing data handling approach, a two-dimensional tipping point analysis will be conducted that will vary assumptions about the missing outcomes on the two treatment arms independently, including scenarios in which dropouts on treatment have worse outcomes than dropouts on placebo.

Other sensitivity analysis, based on data as observed (ie, no imputation on missing values) and Last Observation Carried Forward (LOCF), etc, may be explored and provided. Subgroup analyses by sex, age, and race may be explored and provided as appropriate. Details will be documented in the SAP.

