#### 4.3.1. Primary Estimand

The population of the primary estimand is among participants (aged 4 years or older) with documented evidence of acquired HO and weight gain according to the inclusion/exclusion criteria. Participants will receive either active setmelanotide or placebo, where dose-escalation will occur based upon an **CCI** [REDACTED]. The primary analysis will be executed using the mITT analysis set, including all randomized patients receiving at least one dose of study drug, grouped as randomized.

The variable is mean percent change from baseline in BMI after 52 weeks of treatment with either setmelanotide or placebo.

Intercurrent events: Patients who discontinue treatment prior to study discontinuation will be handled via the treatment policy strategy, in which all collected measurements will be included in the statistical analyses. Other potential intercurrent events such as receiving the wrong treatment, treatment interruption, and non-adherence to study drug will also be handled via the treatment policy strategy whereby all collected measurements will be included in the statistical analyses.

Any on-study death will be handled via the composite strategy, in which death is considered a sufficiently unfavorable outcome and the patient will have their corresponding change and percent change from baseline artificially set to 0.

The population level summary is the difference between treatment groups (setmelanotide and placebo) in mean percent change from baseline in BMI at Week 52, obtained from an analysis of covariance (ANCOVA) model, with unequal variance to account for possible unequal residual variances, based on the outcomes of 100 imputed datasets combined using Rubin's Rule (Little and Rubin 2002). Multiple imputation assuming missing not at random (MNAR) will be used as the primary approach for missing data and will model the missing measurements based on known measurements from retrieved dropouts in the same treatment group. If insufficient retrieved dropouts exist to provide a reliable multiple imputation model, wash-out imputation will be used where missing values for subjects on active drug will be imputed with observed baseline and data from the placebo group. No intermediate values from the active treatment group would be used in this approach. Further technical details are found in [Section 3.10.2](#).

The robustness of the primary estimand will be assessed through sensitivity analysis using two-dimensional tipping point.

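### Protocol 4.3 permits investigators to withdraw consenting patients from the trial for adverse events, non-adherence or non-compliance, which conflicts with the follow-up that the treatment-policy estimand requires

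*Protocol*

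**What the plan says.** Protocol 4.3 gives the site a discretionary power: "The Investigator also has the right to withdraw patients from the trial for reasons such as" three listed items. The first is "AEs, which in the opinion of the Investigator justifies treatment or trial withdrawal". The second is "Non-adherence to trial medication regimen or protocol requirements". The third is non-compliance with instructions or failure to come back for follow-up. On what happens next, the same section says "Patients who withdraw from the trial will attend an ETT visit only". Protocol 5.1.3, like the synopsis, adds: "Patients who discontinue prematurely and withdraw from the trial will not be required to complete the SFV following the ETT".

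Protocol 7.4 sets the rule for the primary analysis. All patients, "regardless of intercurrent events, continue to be measured at each prespecified clinical visit unless consent to collect such data is explicitly withdrawn". Withdrawn consent is the only exception named. SAP 4.3.1 places stopping of treatment under the treatment policy strategy and adds that "treatment interruption, and non-adherence to study drug will also be handled via the treatment policy strategy".

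Protocol 4.3 also contains text that favours retention. It asks for every effort to keep patients enrolled unless safety requires otherwise. It says that patients who stop drug go on with the scheduled visits as Retained Dropouts. It lets doses or visits be skipped without trial withdrawal after consultation with the sponsor and medical monitor.

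**The concern.** Stopping treatment and leaving the trial are different things, and a treatment-policy estimand depends on keeping them apart. Investigator-initiated withdrawal is not withdrawal of consent. Two of the three listed grounds, adverse events and non-adherence, are also what leads to the intercurrent events that the estimand follows through. A site that uses the power as written therefore ends measurement where Protocol 7.4 says it continues.

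Three things are at stake.

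- An outcome lost this way is avoidable, because the patient has not refused further measurement.
- It is unlikely to be lost at random: the reason is tolerability or adherence, which may differ by arm and is plausibly related to BMI.
- The primary imputation (Protocol 7.4, SAP 3.10.2) learns about missing off-treatment outcomes from patients in the same arm who stopped drug and were still measured. Each removal can take a patient out of that group and add one to those who need imputing.

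**Working it through.** **1. The passages side by side**

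| Event in a consenting patient | Protocol 4.3 | Estimand |
|---|---|---|
| Adverse event | may lead to treatment or trial withdrawal | if treatment stops, measurement continues (Protocol 7.4) |
| Non-adherence to drug | may lead to trial withdrawal | treatment policy (SAP 4.3.1); measurement continues (Protocol 7.4) |
| Non-compliance with instructions | may lead to trial withdrawal | not withdrawn consent, so measurement continues (Protocol 7.4) |

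The two columns cannot both be followed once the power is used. The continued-measurement rule stands only in Protocol 7.4; SAP 4.3.1 says that the measurements collected will be included.

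**2. The plan's power figure**

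Inputs from Protocol 7.1 and SAP 3.1: 80 and 40 patients, difference 10 points, SD 10, 20% dropout, two-sided alpha 0.05. After dropout, 64 and 32 remain.

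- SE = 10 × √(1/64 + 1/32) = 2.17.
- Power = Φ(10/2.165 − 1.96) = Φ(2.66) = 99.6%; with the noncentral t it is 99.55%.

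The stated figure of about 99.5% is reproduced.

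**3. Bound on precision**

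- All 80 and 40 observed: SE = 10 × √(1/80 + 1/40) = 1.94.
- Ratio: 2.165/1.936 = 1.12.

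The standard error is about 12% larger with 20% lost than with full follow-up. This is an upper bound at the planned rate, because it counts every dropout as recoverable. Power with full follow-up is 99.9%, so power is not the argument.

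**4. The retrieved-dropout pool**

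The documents do not split the 20% between stopping treatment and leaving the trial. Assume that 20% stop treatment: 0.20 × 80 = 16 active and 0.20 × 40 = 8 placebo.

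The regression in SAP 3.10.2 for the primary-timepoint weight is fitted by arm on six earlier weights (baseline, Visits 2, 4, 7, 9 and 11). With an intercept that is 7 coefficients.

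| Assumed share of those stopping treatment whose outcome is lost | Active retrieved | Placebo retrieved |
|---|---|---|
| none | 16 | 8 |
| half | 8 | 4 |
| three quarters | 4 | 2 |

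If all stay, nothing has to be imputed. If one placebo patient is lost, 7 remain for 7 coefficients, and 7 − 7 = 0 residual degrees of freedom. A few removals could therefore move the primary analysis to the wash-out fallback.

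**5. What could move, on assumed inputs only**

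The shift in the active mean is (number lost/80) × imputation error. With errors of 2.5 to 10 points:

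- 4 lost: 0.125 to 0.5 points;
- 8 lost: 0.25 to 1.0 points;
- 16 lost: 0.5 to 2.0 points.

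Neither input is in the documents, and the direction is unknown.

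If wash-out gives a missing share d of the active arm no benefit, the estimated effect is 10 × (1 − d). The active-arm variance becomes 100 + 100d(1 − d). For d = 0.10 and 0.20 the effect is 9 and 8 points, and power with 80 and 40 is about 99.6% and 98%.

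**The case against.** The best reply is that the protocol already leans towards retention. Protocol 4.3 presses for patients to be kept and has those who stop drug attend all visits. Protocol 5.5.4 answers poor dosing compliance with retraining or nurse administration. The completion categories in Protocol 5.1.6 turn on consent, which fits Protocol 7.4. MNAR imputation, the wash-out fallback and the two-dimensional tipping-point analysis deal with whatever is still missing. All of this stands and lowers the likely number of removals. None of it limits the investigator's power, and the sensitivity analyses recover no data.

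Four stronger readings are tempting, and the documents do not support them.

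- *A reader might infer that missing outcomes are built into the design.* The power is discretionary and discouraged by neighbouring text.
- *A reader might infer that every removed patient loses the primary outcome.* Height, weight and hunger are scheduled at the ETT visit. Under SAP 3.11.1, an on-site value 305 to 425 days after therapeutic dose start can serve as the primary timepoint; under SAP 3.11.2, earlier values can fill the model visits. Late removals need not be missing.
- *A reader might infer that a patient who injects irregularly is both a Retained Dropout and removable.* Protocol 4.3 uses that label for patients who discontinue treatment. Irregular dosing falls under skipped doses and Protocol 5.5.4.
- *A reader might infer that the 14 days after the last dose, which SAP 4.5.2 counts as treatment-emergent, go unobserved in patients removed for an adverse event.* Protocol 6.10 keeps investigators responsible for following events that are serious, related or the cause of stopping drug, and 6.10.3 requires serious events to be followed up. Whether the safety follow-up (SFV) exemption in 5.1.3 reaches investigator-initiated withdrawal is itself unclear: the schema footnote in 1.3 requires that visit after premature discontinuation, and 5.1.4 exempts only certain completers.

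**Conclusion.** The conflict is real and worth correcting. Protocol 4.3 permits removal of a consenting patient for reasons that Protocol 7.4 does not recognise as ending measurement, and SAP 4.3.1 treats two of the resulting events, treatment discontinuation and non-adherence, by treatment policy. Any removal before the primary window creates an avoidable missing outcome, probably related to adherence or tolerability, and depletes the group on which the primary imputation relies.

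The size cannot be derived, because the documents do not say how many patients would be removed. The firm figures are the bound on the standard error (1.94 against 2.17) and power of about 99.5% at the planned dropout rate. The counts of retrieved dropouts rest on applying the 20% rate to treatment discontinuation. The bias figures rest on assumed inputs and show scale only. What is at risk is what the primary analysis estimates and whether its preferred imputation model can be fitted, rather than the chance of a significant result.

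**What to change.** - **Non-adherence and non-compliance.** Reword Protocol 4.3 so that these may end trial treatment but not follow-up. Such patients stay as Retained Dropouts. Follow-up ends only on withdrawal of consent or assent, death, or loss to follow-up under 4.4.
- **Adverse events.** Reconcile the adverse-event item and the safety exception in Protocol 4.3 with 7.4, so that stopping treatment for an adverse event does not by itself end outcome collection in a patient who still consents. No rule on when treatment stops needs to change.
- **Safety follow-up visit.** Reconcile the exemption in the synopsis and 5.1.3 with the schema footnote in 1.3, with 5.1.4 and with 6.10, and state whether it covers investigator-initiated withdrawal.

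The cost is an amendment to wording. Protocol 4.3 already provides for visits by Retained Dropouts. Sites lose some discretion to remove non-compliant patients.
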